Study Procedures: Subjects will have their first study visit at the VA Greater Los Angeles Healthcare System Clinical Research Center (CRC) which will include subject consent and review of the entry criteria. Once consent is obtained, a medical history and physical exam will be performed including height, weight, and measurement of waist to hip ratio (anthropometrics). The urologist's DRE and clinical stage will be recorded from the subject's urology note, and prostate needle biopsy pathology including Gleason grade and percent of cores with cancer will be recorded. A fasting serum specimen will be collected for biomarker studies. A DEXA scan will be performed (to determine lean body mass to calculate caloric intake for the weight loss program) and to determine percent body fat. The Subject will then return home and during the next week will keep a 3-Day Food Diary (Appendix 2). Subject's will be randomized within 3-days of their initial visit and contacted at home with the results of the randomization.

Randomization: If a subject meets all eligibility criteria, the following steps will occur:

1. The study coordinator will FAX the subject's initials, study ID, and date of visit to the junior statistician (to be named).
2. Within 24 hours the statistician will inform the research coordinator of the randomization result (weight loss vs. No Weight Loss Group) and date of randomization. The research coordinator will inform the study subject of the results and schedule subsequent study visits.
3. The randomization will use a permuted block design with 5 blocks of size 13 (7 weight-loss and 6 no weight-loss).

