Immunostaining and Interpretation: Immunostaining of paraffin embedded pretreatment prostate needle biopsy specimens and malignant tissue from radical prostatectomy specimens will be performed using ki67 monoclonal antibodies (DAKO) and a TUNEL assay (BioVision). The cancer tissue with the highest Gleason grade will be analyzed in a blinded fashion by counting 300 cancer cells per slide. Our main objective (Objective 1 of this proposal) will be to compare the percent of cells staining positive for ki67 and TUNEL between the Control Group-No Weight Loss and Weight Loss Group (controlling for Gleason grade). We will also compare the percent of cells staining for ki67 and TUNEL in the prostate needle biopsy specimen relative to the prostatectomy tissue (also matching for Gleason grade). In addition, we will perform correlation analysis to determine if weight loss correlates with proliferation and apoptosis. We hypothesize that with increasing weight loss there will be decreased ki67 staining and an increasing percentage of cells with TUNEL staining. To further evaluate the effect of weight-loss on prostate tumor staining of the IGF signaling cascade we will analyze immunostaining of phospho-IGF-1R (using a Cell Signaling antibody) and phospho-Akt (Cell Signaling). We will also evaluate for earlier stages of apoptosis as measured by activated caspase-3 (Oncogene). If we detect changes in apoptosis, we will also stain for BAX and BCL2 using antibodies from R&D. If we detect changes in proliferation as measured by ki67 staining, we will also stain for Mcm-2 (which has been shown to be a prognostically important prostate cancer proliferation marker) using antibodies from R&D.⁶⁶

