Statistical Design: The statistical design of this study is a randomized repeated measures utilizing random mixed block sizes known only to the statistician constructing the randomization list to assign subjects to two study arms in a ratio of 7:6, weight loss to no weight loss.

Sample Size Determination: An evaluable sample of at least 60 subjects (no weight loss=30, weight loss=30) is expected to provide 80% power to detect an effect size of 0.74 using a two group t-test with a 0.050 two-sided significance when comparing the apoptotic index (primary outcome variable) in the radical prostatectomy malignant epithelium between the weight loss and no Weight Loss Group. The apoptotic index will be measured in the malignant epithelium with the highest Gleason grade. To account for a post-randomization attrition rate of up to 15% in the Weight Loss Group, a total of 35 subjects will be randomized to the Weight Loss Group, thus bringing the total sample size to 65 subjects. Kim et al. observed an effect size of 1.74 on apoptotic index using a nutritional intervention in a similar study.⁶⁴

Data Analysis: Data analyses will be performed on randomized subjects who complete the study. All parameters measured will be summarized descriptively. The number of subjects, mean, standard error of the mean, median and min-max values will be presented for continuous parameters and the number and percentage of subjects in each category will be presented for categorical parameters. No imputation of missing data is planned. Demographic and baseline characteristics will be summarized using descriptive statistics overall and by treatment group to assess baseline comparability. Treatment groups will be compared using the appropriate nonparametric tests for categorical parameters and analysis of variance models for continuous parameters.

Primary Outcome Variable: The primary outcome variable is apoptotic index of the highest Gleason grade malignant epithelium in the radical prostatectomy specimen. The primary objective is to compare the mean apoptotic index between the Weight Loss Group and the Control Group-No Weight Loss. The two independent sample t-test will be used to compare the index between the groups. If the index is non-normally distributed we will use the Wilcoxon rank sum test. Next, linear regression models will be constructed to test whether the treatment effect

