is significant after controlling for Gleason grade, stage and any demographic factors that are significantly different between the groups.

Secondary Outcome Variables: The secondary outcome variables are: the proliferative index in prostate cancer epithelium obtained from the radical prostatectomy specimen, the change in apoptotic and proliferative indices of malignant epithelium between the diagnostic prostate needle biopsy and corresponding radical prostatectomy, the change (baseline vs post-intervention) in serum IGF-related analytes: IGF-1 and IGFBP-1, the ex-vivo mitogenic and apoptotic activity of patient sera on LNCaP cells, and the change in body weight and percent body fat by DEXA over 4-9-weeks.

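### The adjusted regression of the apoptotic index picks its demographic covariates by significance, leaves out the planned biopsy index, and is not ranked against the t-test

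*Combined protocol and SAP*

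**What the plan says.** All places are in section 3 (Work Proposed) of the combined protocol and SAP.

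- **Primary Outcome Variable.** "The primary objective is to compare the mean apoptotic index between the Weight Loss Group and the Control Group-No Weight Loss". For this, "The two independent sample t-test will be used to compare the index between the groups"; the Wilcoxon rank sum test replaces it if the index is not normal, with no criterion given.
- **Same paragraph, next step.** Linear regression then tests whether the treatment effect "is significant after controlling for Gleason grade, stage and any demographic factors that are significantly different between the groups".
- **Immunostaining and Interpretation.** "Immunostaining of paraffin embedded pretreatment prostate needle biopsy specimens and malignant tissue from radical prostatectomy specimens will be performed", for both Ki67 and TUNEL. "The cancer tissue with the highest Gleason grade will be analyzed in a blinded fashion by counting 300 cancer cells per slide". The main comparison is described as one "between the Control Group-No Weight Loss and Weight Loss Group (controlling for Gleason grade").
- **Study Procedures.** At the first visit "prostate needle biopsy pathology including Gleason grade and percent of cores with cancer will be recorded", and the urologist's "DRE and clinical stage will be recorded".
- **Secondary Outcome Variables.** The biopsy index appears only in a change score from biopsy to prostatectomy.
- **Secondary Statistical Analyses.** A further model for each tissue marker uses group, grade, PSA, percent body fat and demographics. The biopsy index is not listed there either.
- **Data Analysis.** The analysis set is men who complete the study, and missing values are not imputed.

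**The concern.** A significance test of baseline differences does not identify the covariates worth adjusting for. In a randomized comparison it responds to imbalance, whether or not the factor predicts the outcome, and it can pass over a strong predictor that happens to be balanced. The content of the adjusted model is then unknown until the arms have been compared.

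The baseline value of the outcome itself, which is the natural covariate to consider, will be measured but is not in the model. Grade and stage could be read as the baseline values or as those found at surgery. Surgical values are obtained after randomization and after the intervention, so adjusting for them answers a different question.

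Finally, the plan does not say what follows if the unadjusted and adjusted results disagree. At stake are the reproducibility of the adjusted result and possibly some precision, in a trial of 60 evaluable men powered only for an effect size of 0.74.

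**Working it through.** **Inputs from the plan.** 30 evaluable men per arm, effect size d = 0.74, two-sided alpha 0.05, 300 cells counted per slide. **Assumed, because the documents do not give them:** the biopsy-to-prostatectomy correlation r, the number of demographic factors k, the mean and spread of the index, and the normality check.

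**1. The plan's own figure.** Noncentrality = 0.74 / sqrt(2/30) = 2.87 on 58 df. Power = 80.5%, against 80% stated. It reproduces.

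**2. How often chance changes the model.** P(at least one significant factor) = 1 - 0.95^k for independent factors:
- k = 3: 1 - 0.857 = 14%
- k = 5: 1 - 0.774 = 23%

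This is how often the model changes, not an error rate. It describes fully randomized arms; imbalance among completers need not be chance alone.

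**3. What the rule forgoes.** Simulation with one baseline covariate correlated r with the outcome, 30 per arm, 3,000 runs per setting, d = 0.74:

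| r | t-test | adjust only if imbalance has p < 0.05 | always adjust |
|---|---|---|---|
| 0.3 | 80% | 80% | 84% |
| 0.5 | 78% | 79% | 89% |
| 0.7 | 81% | 83% | 97% |

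The rule's null rejection was 3.7% to 4.2%. It does not inflate error; it gives up most of the available precision.

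**4. Adding the biopsy index.** Formula: effect d / sqrt(1 - r²) on 57 df. Change score: d / sqrt(2(1 - r)) on 58 df, equal SDs assumed. The last two columns come from 120,000 simulated normal trials per r, with the model containing arm, biopsy index and an uninformative three-level ordinal grade. They show percentage points of power against the t-test.

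| r | ANCOVA, formula | change score | simulated, complete | simulated, 10% of biopsies missing* |
|---|---|---|---|---|
| 0 | 80.4% | 51% | -1.4 | -2.2 |
| 0.2 | 82.0% | 61% | +0.1 | -0.8 |
| 0.3 | 84.0% | 66% | +2.2 | +1.1 |
| 0.5 | 90.2% | 80% | +8.4 | +7.0 |

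*Pooled mean fill plus missing indicator. Null rejection at r = 0.3 was 5.1% complete and 5.0% with missing values.

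Break-even r is about 0.20 with complete data and 0.25 with 10% missing. The planned change score does not beat the t-test unless r exceeds 0.5.

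**5. Cost within the planned regression.** Grade and stage are already in it, so only the biopsy term and the indicator are new. At r = 0, two uninformative terms cost 1.4 points, or about 1.4 / 2 = 0.7 each, and the indicator with missing values costs 2.2 - 1.4 = 0.8. The added cost is therefore about 0.7 to 1.5 points. Clinical stage was not in the simulated model; it would lower the figures against the t-test by roughly a further 0.7.

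**6. Counting noise.** With 300 cells, an assumed mean index of 1% to 5% and a between-man CV of 0.5 to 1.0:
- a latent r of 0.3 is observed as about 0.11 to 0.25, and a percent-scale model changes power against the t-test by -1.7 to +1.0 points;
- a latent r of 0.5 is observed as about 0.21 to 0.44, with a change of -0.2 to +6.5 points.

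**7. If either result could count.** Null rejection for t-test or adjusted model was 6.0%, 7.0% and 8.2% at r = 0.3, 0.5 and 0.7.

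**8. Against the plan as written.** The planned procedure includes the Wilcoxon switch. In the 300-cell settings, with Shapiro-Wilk at 0.05 assumed as the check, Wilcoxon is chosen in 68% to 100% of trials. A percent-scale primary ANCOVA then loses about 8 to 15 points under additive effects with CV 1.0 and gains about 10 to 17 under proportional effects.

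**The case against.** The hierarchy is readable as it stands: the sample size is computed for a t-test, the t-test comes directly after the primary objective, and the regression is introduced as a later step. The demographic rule therefore touches only a follow-on model, and the separate tissue-marker model already takes demographics without a significance filter. The correlation r is unknown, some biopsies may not yield a usable count, and the gain may be nil. All of this stands. It limits the point to the regression and to an explicit ranking; it does not defend choosing covariates by significance.

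Three stronger readings are tempting and are not supported:

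- **That the primary test should become an ANCOVA.** Omitting a covariate does not invalidate the t-test, and step 8 shows that the replacement could lose or gain 10 points or more, depending on the shape of the effect.
- **That the immunostaining paragraph contradicts the statistical section on Gleason adjustment.** That paragraph goes on to speak of also matching on grade when comparing biopsy with prostatectomy, and the RNA and protein section matches tissue grade. Controlling may mean matching the tissue, and a grade-adjusted regression is planned in any case. This is an ambiguity to clear up.
- **That the plan inflates type I error.** Nowhere does it say that either result would count as success. The 6% to 8% is what the open wording would permit.

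**Conclusion.** The concern holds for the adjusted regression. Its covariates are chosen on observed imbalance, with a 14% to 23% chance of a changed model for 3 to 5 independent demographics. It omits a baseline that is already planned, and it leaves the timing of grade and stage unstated. Adding the biopsy index is worth about 2 points of power against the t-test at an observed r of 0.3 and about 8 at 0.5, under normal outcomes. It is worth nothing at or below about 0.2, and possibly nothing once counting noise is allowed for. The case for fixing the covariates and ranking the analyses does not depend on r.

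The t-test's 80% power reproduces. A reader might infer that the test is therefore also unbiased. That is not claimed here: the analysis set is completers only, with attrition of up to 15% provided for in the Weight Loss Group alone, and this check did not examine what that does to the comparison.

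**What to change.** 1. In the regression under Primary Outcome Variable, delete the clause that admits demographics by significant group difference. Fix the covariates in advance as biopsy apoptotic index, biopsy Gleason grade and clinical stage, plus any demographics named beforehand on prognostic grounds.
2. State that grade and stage are the baseline values recorded under Study Procedures. Use the grade of the analysed surgical tissue only in a sensitivity analysis.
3. For the biopsy index only, amend the no-imputation rule: fill missing values with the pooled mean and add a missing indicator, so that no man with a prostatectomy index is lost. Under complete-case analysis, losing a share of men of about r² would cancel the gain.
4. State that the t-test or Wilcoxon comparison is the deciding primary analysis and that the regression is supportive. Say how non-normality will be judged, since otherwise the deciding test is still open.
5. Reword the immunostaining paragraph to match, making clear whether controlling for grade means tissue matching or a model term.

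The change is wording only: biopsy staining, biopsy grade and clinical stage are already planned. If the covariates carry no information, the adjusted model loses about 1 to 2 points of power. The deciding test and the sample size are untouched.

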Secondary Statistical Analyses: The statistical methods for these analyses will be analysis of variance (ANOVA), linear regression, and correlation analysis. ANOVA will be used to determine if the serum biomarkers (IGF-I, IGFBP-1, proliferation and apoptosis bioassays) change over the course of time. These models will include a term for time, treatment (weight-loss versus no weight loss) and the time by treatment interaction effect. We will also construct ANOVA models for weight and body fat over time to determine if the treatment by time effect (intervention effect) is significant. Next, linear regression models will be constructed for each biomarker to assess the factors that predict change in that marker. Predictors will include actual weight loss (percent change), group, grade, PSA, percent body fat, and demographic factors. These models will allow us to assess the direct effect of weight loss on each of the serum biomarkers and allow for the assessment of whether weight change or intervention is the primary factor predicting change in the biomarkers. This assessment is required due to the fact that the intervention will have varying effects on weight based on the amount of subject compliance with the weight loss regime. Regression models will also be constructed to compare the groups with respect to the pre-prostatectomy biomarkers and the tissue markers and the between group tissue markers (apoptosis, Ki67 staining). A separate model will be constructed for each marker including the predictors of group, grade, PSA, percent body fat and demographic factors. Next, we will construct regression models to determine if the biomarkers, or change in biomarkers, affect the post-op pathology. Ordinal regression will be used for post-op pathology. These models will include terms for the demographic factors and for each of the biomarkers. Since there are a large number of biomarkers we will first construct single biomarker models which will include the covariates for each outcome and then combine together all significant markers into multiple regression models. Finally, we will use the Spearman correlation to test for correlations between pre-prostatectomy biomarkers and the tissue markers. This analysis will specifically address **Objective 3** of the proposal, that being to determine if a correlation exists between serum biomarkers and tissue biomarkers. The Spearman correlation is a non-parametric rank based correlation measure that does not depend on the assumption that the markers are normally distributed.

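### For the serum markers and ex-vivo bioassays, the planned time-by-treatment ANOVA is a change-score test; adjusting for each marker's own baseline would usually be more precise at almost no cost

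*Combined protocol and SAP*

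**What the plan says.** All references are to section 3 (Work Proposed) of the combined protocol and SAP.

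- **Outcomes.** Secondary Outcome Variables lists "the change (baseline vs post-intervention) in serum IGF-related analytes: IGF-1 and IGFBP-1", together with the ex-vivo activity of patient sera on LNCaP cells and the change in weight and DEXA percent body fat.
- **Test for the serum markers and bioassays.** Secondary Statistical Analyses specifies ANOVA: "These models will include a term for time, treatment (weight-loss versus no weight loss) and the time by treatment interaction effect".
- **Test for weight and body fat.** The same paragraph plans "ANOVA models for weight and body fat over time to determine if the treatment by time effect (intervention effect) is significant".
- **Two further regressions on the serum markers.** One models change in each marker on achieved percent weight loss, group, grade, PSA, percent body fat and demographics. The other compares the arms on pre-prostatectomy markers using group, grade, PSA, percent body fat and demographics. Neither lists the marker's own baseline value.
- **Measurement times.** The flow chart, its footnotes and the serum studies overview give one baseline and one pre-surgery serum sample in both arms. DEXA follows the same pattern. Weight does not: the weight-loss arm is weighed at every weekly visit, the control arm only at the first and final visits.
- **Analysis set.** "Data analyses will be performed on randomized subjects who complete the study", with no imputation; the target is 30 evaluable men per arm.

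**The concern.** With only two time points, a time-by-treatment interaction carries no information beyond the difference between arms in mean change. Subtracting the baseline amounts to regressing the post value on baseline with the slope set to 1. If the true slope is below 1, as it is when variances are equal and r is below 1, the subtraction over-corrects whatever chance baseline difference is present and carries extra baseline noise into the comparison. Estimating the slope removes that noise.

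The baseline values are already collected, and the plan already intends to adjust for other covariates, yet it omits the one most directly tied to each outcome. These comparisons are central to Objective 2. The sample-size section powers only the apoptotic index, so the serum outcomes have no stated power and precision should not be given away.

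**Working it through.** **1. The plan's own figure.** Sample Size Determination states that the evaluable sample is "expected to provide 80% power to detect an effect size of 0.74 using a two group t-test with a 0.050 two-sided significance". With 30 per arm, the noncentral t with 58 degrees of freedom gives 80.5% power at 0.74, and the effect with exactly 80% power is 0.736. The stated figure reproduces. It applies to the apoptotic index only and is used below solely as a benchmark.

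**2. Equivalence.** On a simulated 30 + 30 data set with two time points, the interaction F was 14.135 and the squared change-score t was 14.135.

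**3. Could another planned model already use the baseline?**
- The ANOVA has a separate treatment term, so baseline means are not constrained equal, and it does not recover the precision in that way.
- The regression on change omits the marker's baseline. It also conditions on achieved weight loss, which is a consequence of the intervention, so its group coefficient is not the total between-arm effect.
- The regression on pre-prostatectomy markers omits the marker's baseline.

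**4. Variances.** Let s0 and s1 be the baseline and post standard deviations and r their correlation.
- Change score: s0² + s1² − 2·r·s0·s1
- ANCOVA: s1²(1 − r²)
- Difference: (s0 − r·s1)², which is never negative.

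So in large samples the direction does not depend on equal variances. With s0 = s1 = s, the variances are 2s²(1 − r) and s²(1 − r²), and the ratio is (1 + r)/2.

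**5. Small-sample cost.** Estimating the slope costs one degree of freedom (57 instead of 58) and inflates the variance by about 1 + 1/56 = 57/56. The ratio becomes (1 + r)/2 × 57/56.

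**6. Power.** Take a contrast with 80% power under the planned test. Its noncentrality is 0.7356/√(2/30) = 2.849. Under ANCOVA this is divided by the square root of the ratio in step 5.

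| r (assumed) | (1 + r)/2 | × 57/56 | Noncentrality | ANCOVA power |
|---|---|---|---|---|
| 0.3 | 0.650 | 0.662 | 3.50 | 93.1% |
| 0.5 | 0.750 | 0.763 | 3.26 | 89.4% |
| 0.7 | 0.850 | 0.865 | 3.06 | 85.3% |
| 0.9 | 0.950 | 0.967 | 2.90 | 81.3% |
| 0.95 | 0.975 | 0.992 | 2.86 | 80.3% |
| 0.98 | 0.990 | 1.008 | 2.84 | 79.7% |

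The break-even in variance is (1 + r)/2 × 57/56 = 1, that is r = 112/57 − 1 = 0.965.

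**7. Simulation.** With 20,000 simulated trials at each r, power for the change-score test and ANCOVA was 80.0% and 88.9% (r = 0.5), 80.7% and 85.8% (r = 0.7), and 79.8% and 80.9% (r = 0.9).

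**The case against.** The strongest reply is that the planned test is valid. Under randomisation a change-score comparison is unbiased and keeps its type I error, and it matches the way the plan defines these outcomes, as changes. That stands: the point concerns efficiency. It does not decide against baseline adjustment, because with baseline in the model the group coefficient is the same whether the response is the post value or the change.

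The size depends wholly on r, which the documents do not give, and the 80% starting point is borrowed from the primary outcome. This also stands, and is why a range is shown. Equal variances may fail for IGFBP-1, which the Background describes as changing up to fifty-fold with fasting. The direction in step 4 survives in large samples; the percentages may not. The scale for that marker is a separate question that arises equally for the planned ANOVA.

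A reader might infer four stronger things that the documents do not support:
- **That the planned test ignores chance baseline imbalance.** It subtracts the baseline; the weakness is the fixed slope.
- **That Objective 2 rests on this test alone.** Two regressions with a group term address the same markers, although neither includes the marker's baseline.
- **That weight also has a single post value.** The weight-loss arm is weighed weekly, and the plan does not say which visits enter the weight ANOVA, so equivalence to a change-score t-test is not established there.
- **That power is materially lost for weight and body fat.** If r is 0.9 or more over 4 to 9 weeks, which is an assumption, the gain is about one point or nil.

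**Conclusion.** The point holds as an efficiency improvement for IGF-1, IGFBP-1 and the two bioassays. Relative to a planned test with 80% power at 30 per arm, baseline adjustment adds about 13, 9, 5 and 1 percentage points at r = 0.3, 0.5, 0.7 and 0.9, and nothing above about 0.96. These figures assume equal variances and a value of r that the documents do not supply. For percent body fat, and for weight once its time points are fixed, the same reasoning applies but the gain may be negligible. The outcomes are secondary, the planned test is not biased, and nothing here bears on the primary analysis or on the 65 men to be randomised.

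**What to change.** In Secondary Statistical Analyses, for each serum marker and bioassay:

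- Make the between-arm test an ANCOVA of the pre-surgery value on group plus the same marker's baseline value.
- Leave achieved weight loss out of this model; keep it for the separate regression on predictors of change.
- Report the adjusted mean difference with its 95% CI.
- Retain the time-by-treatment ANOVA as descriptive.

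The same model may be used for percent body fat and weight. For weight, name the baseline and final pre-surgery values, the only ones common to both arms, as the values analysed.

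The cost is a change of SAP wording and one degree of freedom per model. No additional data, visits or men are needed.

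### The serum-biomarker regressions put percent weight change beside group, and so cannot show a direct effect of weight loss or which of the two is the primary factor

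*Combined protocol and SAP*

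**What the plan says.** All references are to the combined protocol and SAP, section 3 (Work Proposed).

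- **Secondary Statistical Analyses, serum markers.** A treatment-by-time ANOVA comes first. Regressions for change in each biomarker follow: "Predictors will include actual weight loss (percent change), group, grade, PSA, percent body fat, and demographic factors". Two readings are claimed for them: a direct effect of weight loss on each serum marker, and that they "allow for the assessment of whether weight change or intervention is the primary factor predicting change in the biomarkers". The plan calls this assessment required because weight loss will vary with compliance. It states no mediation method, no assumption about confounding and no sensitivity analysis.
- **Secondary Statistical Analyses, tissue markers.** "A separate model will be constructed for each marker including the predictors of group, grade, PSA, percent body fat and demographic factors". Weight change is not in this list. No time point is given for PSA or percent body fat.
- **Secondary Outcome Variables.** The list includes "the change in body weight and percent body fat by DEXA over 4-9-weeks", so weight and body fat are themselves treated as outcomes of the intervention.
- **Weight Loss Intervention Group.** Expected loss is 4-6% of body weight. The same programme prescribes 20-25% of energy from fat and an hour of exercise a day. The control-group section expects no weight loss of any significance.

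**The concern.** Randomization protects the comparison of groups. It does not protect the comparison of men who lost more weight with men who lost less. Men who follow the programme closely differ in weight loss, but also in diet composition and exercise, and the protocol's own background section says that low-fat diet and exercise raise IGFBP-1. Once weight change is in the model, the group coefficient is no longer the intervention effect. The weight coefficient is a within-arm association that mixes any causal effect of weight with whatever else drives both.

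At stake is the interpretation under Objective 2. Weight loss could be credited with an effect it does not have, or an intervention that works by another route could be reported as doing nothing beyond weight.

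**Working it through.** **1. The plan's own figure.** Under Sample Size Determination, the plan says that 30 evaluable men per arm "is expected to provide 80% power to detect an effect size of 0.74". That figure is for the primary comparison, a t-test at two-sided 0.05. Exact noncentral-t power at 30 per arm and effect size 0.74 is 80.5%, so the figure reproduces. It belongs to the primary test. The plan gives no power for the regressions, and 0.74 is used below only as a scale.

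**2. Inputs.**
- From the documents: 30 per arm; two-sided 0.05; mean difference in percent weight loss m = 5 points (midpoint of 4-6%, controls about 0).
- Assumed: within-arm SD of percent weight loss s = 2 or 3 points; within-arm correlation r between weight loss and marker change of 0.09 to 0.3. Both are taken as equal in the two arms. If weight loss and marker each correlate 0.3 with a shared cause, r = 0.3 × 0.3 = 0.09. Pairs 0.5/0.3 and 0.5/0.5 give 0.15 and 0.25. The value 0.3 is the upper case.
- Marker change is scaled to within-arm SD 1, with positive values favourable and weight loss coded positive.

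**3. Bias.** With group in the model, the weight coefficient is the pooled within-arm slope, r/s when weight has no causal effect. Therefore:

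adjusted group effect = true group effect − r × m / s

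spurious weight part = r × m / s

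**4. No intervention effect on the marker.** The shared cause here must be something present equally in both arms, such as general health behaviour. Estimates are from the formula. Rejection rates are from simulations of 6,000 trials per setting.

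| r | s | Adjusted group effect | Group significant | Weight falsely significant |
|---|---|---|---|---|
| 0.09 | 2 | −0.09×5/2 = −0.225 | 7-8% | 10% |
| 0.09 | 3 | −0.09×5/3 = −0.15 | 7-8% | 11% |
| 0.15 | 2 | −0.375 | 15% | 22% |
| 0.15 | 3 | −0.25 | 11% | 22% |
| 0.25 | 2 | −0.625 | 34% | 49% |
| 0.25 | 3 | −0.42 | 25% | 48% |
| 0.3 | 2 | −0.75 | 45% | 65% |
| 0.3 | 3 | −0.50 | 33% | 65% |

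Without weight change in the model, the group test rejects in about 5% throughout.

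**5. Can the model tell which factor is primary?** Take a true group effect of 0.74 and s = 2.
- Effect wholly through weight, no confounding: adjusted group about 0 (significant in 5%), weight significant in 61%.
- Effect not through weight at all, r = 0.3: adjusted group 0.74 − 0.75 = −0.01, weight significant in about 65%.

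Opposite truths give nearly the same output. At r = 0.09 the second case is milder: 0.74 − 0.225 = 0.515. If half the effect runs through weight and there is no confounding, group and weight are each estimated at 0.37, with power of 15% and 20%.

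**6. Precision.** The variance inflation for group is 1 + m²/(4s²). That is 1 + 25/16 = 2.56 at s = 2 and 1 + 25/36 = 1.69 at s = 3. Even without confounding, power for a non-weight effect of 0.74 falls from about 80% to 42% and 58%.

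**The case against.** The strongest reply is that intervention effects are estimated elsewhere, without these covariates. The primary outcome uses a t-test or Wilcoxon test, then regression on grade, stage and imbalanced demographics. Serum markers have the treatment-by-time ANOVA. The section on immunostaining plans a Ki67 and TUNEL comparison controlling for Gleason grade. All of this stands. A reader might infer that the plan removes the effect the trial is meant to find. The documents do not support that: the weight-change model is a later, additional step.

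A reader might also infer that Objectives 1 to 3 all rest on these models. They do not. Weight change enters only the serum-marker models, Objective 3 is assigned to Spearman correlation, and the next trial is tied to tissue proliferation and apoptosis.

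Third, the tissue-marker models might be read as adjusting for post-intervention PSA and body fat. The text gives no time point. Both are measured at baseline as well as before surgery, and baseline values would be valid covariates. What stands is an ambiguity to be closed.

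Fourth, the plan's direct effect is that of weight loss, not of group. If everything runs through weight, a null adjusted group term is the correct conditional answer. That is fair, but it does not rescue the claim, because weight loss is not randomized and the plan states no assumption that would identify its effect.

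Finally, the large error rates depend on r, which the documents do not give. This also stands, and the range is shown for that reason.

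**Conclusion.** The point holds for the serum-biomarker change models and for the two conclusions drawn from them. Given a positive shared cause, the adjusted group effect is biased downward and the weight effect upward, whatever the exact inputs. The size rests on the assumed SD and correlation: from a small distortion (about −0.15 SD, group significant in 7-8%) to a serious one (−0.75 SD, 45%). The figures show range and direction; they do not predict what this trial would find.

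The primary result is not at risk, no stated figure is wrong, and the tissue-marker part is a missing time point rather than a demonstrated error. It should still be corrected, because the plan calls the assessment required and does not label it exploratory.

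**What to change.** 1. Take every reported group effect on a serum or tissue marker from a model with group and pre-randomization covariates only: baseline marker where available, baseline PSA, baseline percent body fat and biopsy grade.
2. State in the tissue-marker models that PSA and percent body fat are baseline values.
3. Keep the weight-change models, labelled as exploratory associations that do not estimate an intervention effect. They need not be removed. Running them within each arm would not cure the confounding, since with group in the model the weight coefficient is already a pooled within-arm slope.
4. Delete the claims about a direct effect of weight loss and about the primary factor.

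The cost is SAP wording only, with no added patients, visits or assays. The plan gives up a mechanistic claim that its data cannot support.
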